## Study Procedures

- Program Adaptation and Implementation:
- For this project, we will use the Nourishing the Community through Culinary Medicine curriculum that is available on our Nourish website: <https://sph.uth.edu/research/centers/dell/nourish/research-resources/toolkit>
- The table below outlines the topics and objectives for the 5 NCCM sessions:

Session	Cooking Technique	Topics and Materials	Learning Objectives	SCT Change Objectives
1	Roasting vegetables and steaming grains.	Handouts: Healthy Eating; Goal setting.  Videos: My Plate is Your Plate; Small Changes for Health.	

• Use safe and effective knife skills to cut a variety of vegetables.

• Discuss challenges with managing diabetes.

• Identify a healthy plate as <math>\frac{1}{2}</math> fruits and vegetables, <math>\frac{1}{4}</math> lean protein, and <math>\frac{1}{4}</math> whole grains.

• Understand how to set realistic goals.

• Learn how to prepare a balanced family meal.

	

2	Cooking grains pilaf-style and baking.	Handouts: Diabetes management; Carbohydrate counting; Label reading.  Videos: All About Carbohydrates; Low Blood Glucose; High Blood Glucose.	
 
• Use safe and effective knife skills to cut a variety of vegetables.
 
• Describe what foods and beverages contain carbohydrates.
 
• Learn how to control blood sugar levels using a MyPlate approach.
 
• Learn how to prepare a balanced family meal.
 
	
 
• Outcome expectations of the taste of healthy foods.
 
• Knowledge of healthy eating.
 
• Self-efficacy of preparing healthy foods.
 
• Perceived social support for healthy eating.
 
• Normative beliefs of healthy food.
 

3	Soups, stews, and preparing dressings.	Handouts: Healthy habits for the family  Videos: A Family Affair Why Beverages Matter.	
 
• Use safe and effective knife skills to cut a variety of vegetables.
 
• Practice strategies to develop healthy and mindful habits with family.
 
• Learn how to prepare a balanced family meal.
 
	
4	Sautéing, stir frying, and steaming grains.	Handouts: Planning Healthy Meals  Videos: How to Stock a Healthy Pantry; How to Read Nutrition Facts Labels.	
 
• Use safe and effective knife skills to cut a variety of vegetables.
 
• Practice strategies meal planning and grocery shopping.
 
• Practice reading food labels to encourage better food purchases.
 
• Prepare a balanced family meal.
 
	
5	Sautéing, stir frying, and microwave cooking.	Handouts: Mindful eating.  Videos: Beyond the Scale Mindful Eating Techniques.	
 
• Use safe and effective knife skills to cut a variety of vegetables.
 
• Practice strategies to develop healthy and mindful habits to control blood sugar.
 
• Describe plans to focus on health versus weight.
 
• Prepare a balanced family meal.
 
	

- To conduct the program virtually, we will do the following
  - First, classes will be streamed live from UTHealth Nourish Program’s Teaching Kitchen via Zoom or WebEx platform. Participants will cook and engage virtually (with video and sound on) from their home kitchens via the digital platform.
  - Second, participants will be located across Houston, limiting the ability to provide a “grocery bag”. Participants will be provided a \$40 grocery card and shopping list per class (5 classes for a total of \$200) to purchase ingredients for the cooking sessions. The grocery lists will provide tips and insight to help participants navigate shopping for ingredients.
  - Third, asynchronous virtual educational content (cooking skills videos, animated nutrition education videos, and additional recipes) will be provided to engage and retain participants beyond initial sessions (available at website link).
  - Fourth, to ensure opportunities for participants to engage, classes will be offered during convenient time for participants and recipes will provide enough food for a family of four.
  - Fifth, cohorts will be conducted in either English or Spanish to include a large percentage of clinic patients.
- UTHealth staff will call participant one week prior to classes starting to confirm attendance. If patient confirms attendance, UTHealth staff will send email with class information and gift card-

code, grocery list, recipes, etc. UTHealth staff will call patients the day before class and send a text reminder 2 hours prior to the class start time.

- The virtual curriculum will include five 90-minute sessions (to be held weekly or bi-weekly). Participants will also be expected to shop for groceries ahead of the sessions to participate in the program. A gift card will be provided for groceries (\$40 per class = \$200 total).
- Partnership with UT Physicians sites will allow use of Electronic Medical Record (EMR) data: patient level data for HbA1c, Body Mass Index, Blood Pressure, HDL, LDL and Triglycerides collected as part of their regular standard of care and documented within the EMR. No additional visits, screenings or time will be necessary for participation in the program. Data will be abstracted and shared by clinic site to UTHealth at: baseline (within 90 days of starting the NCCM program) and at program completion (within 90 days of NCCM program completion).
- Informed consent will be obtained electronically via REDcap prior to survey administration. Participants will review the consent documents. Participants will be allowed to contact the Study Coordinator with any questions prior to completing the consent form or the survey. Participants will be allowed to leave the project at any time.
- Participants will be asked to complete an electronic 15-minute survey via REDcap at two timepoints: pre-test survey before the first class and a post-test after the conclusion of the program. The electronic pre- and post-test surveys will collect information on 1) dietary intake, 2) cooking skills, 3) cooking-related psychosocial constructs, 4) diabetes management, and 5) demographics (age, sex, race/ethnicity, education, employment status, preferred language spoken at home, and participation in government assistance programs will be collected at baseline at the start of the program). Survey items are described in detail in the measurement resource table below.

Primary Outcome- measured at both pre-survey (baseline) and post-intervention (follow-up)		
HbA1c	Measured by the clinic at baseline and follow-up	
Secondary Outcomes- measured at both pre-survey (baseline) and post-intervention (follow-up)		
Other clinical measures	Body Mass Index (height and weight), Blood Pressure, HDL, LDL and Triglycerides measured by the clinic at baseline and follow-up	
Variable (Construct)	Number of items and sample question	Source citation
Perceived Health	1 item E.g. Overall, how would you rate your health in the past four weeks? Response options (1-6) – Excellent to Very Poor	Bowling, A; Just one question: If one question works, why ask several? Journal of Epidemiology & Community Health (2005); 59:342-345.
Fruit & Vegetable consumption	2 item E.g. How many servings of VEGETABLES do you eat or drink each day? Response options (0 to 5): None to 4+ servings per day	Yaroch AL, et al. Evaluation of Three Short Dietary Instruments to Assess Fruit and Vegetable Intake: The National Cancer Institute's Food Attitudes and Behaviors Survey. J Acad Nutr Diet. 2012 Oct;112(10):1570-7.(Link: http://www.ncbi.nlm.nih.gov/pubmed/23017567 )
Whole grain consumption	1 item E.g. How many servings of Whole Grains do you eat each day? Response options (0 to 5): None to 4+ servings per day	Adapted from: Yaroch AL, et al. Evaluation of Three Short Dietary Instruments to Assess Fruit and Vegetable Intake: The National Cancer Institute's Food Attitudes and Behaviors Survey. J Acad Nutr Diet. 2012 Oct;112(10):1570-7.(Link: http://www.ncbi.nlm.nih.gov/pubmed/23017567 )

Typical food consumption behaviors	7 items: E.g. How often do you typically eat a green salad? Response options (0-4): Not at all to More than once a day	Pinard, Courtney A., et al. "Development and testing of a revised cooking matters for adults survey." American journal of health behavior 39.6 (2015): 866-873.
Perceived Barriers of Eating Fruits and Vegetables	13 items E.g. I don't eat fruits and vegetables as much as I like to because they cost too much Response options (0-4): Strongly agree to strongly disagree	Pinard, Courtney A., et al. "Development and testing of a revised cooking matters for adults survey." American journal of health behavior 39.6 (2015): 866-873.
Eating/cooking/using nutrition labels	10 items E.g. How often do you compare prices before you buy food? Response options (1-5): Never to Always	Pinard, Courtney A., et al. "Development and testing of a revised cooking matters for adults survey." American journal of health behavior 39.6 (2015): 866-873.
Barriers to Healthy Eating	4 items E.g. Cooking healthy food is difficult Response options (1-5): Strongly agree to strongly disagree	Not Previously validated, pilot tested in APHL
Self-efficacy in cooking food and meal planning	5 items E.g. How sure are you that you could use basic cooking techniques (e.g. microwaving, sautéing, roasting). Response options (0-4): Not at all sure to Extremely [name]., Williams, J.E., Catalano, P.M., & Griffin, S.F. (2011). Development of psychosocial scales for evaluating the impact of a culinary nutrition education program on cooking and healthful eating. Journal of Nutrition Education and Behavior, 43, 511-516.
Diabetes management	16 items E.g. The following statements describe self-care activities related to your diabetes. Thinking about your self-care over the last 8 weeks, please specify the extent to which each statement applies to you.	Schmitt, A., Gahr, A., Hermanns, N., Kulzer, B., Huber, J., & Haak, T. (2013). The Diabetes Self-Management Questionnaire (DSMQ): development and evaluation of an instrument to assess diabetes self-care activities associated with glycaemic control. Health and quality of life outcomes, 11(1), 1-14.
Tertiary - measured at both pre-survey (baseline) and post-intervention (follow-up)		
Nutrition knowledge	1 item E.g. When thinking about preparing a plate of food, how much of your plate should be filled with fruits and vegetables?	Not previously validated, pilot tested in APHL

Covariates- baseline only		
Food Insecurity	2 items e.g., "Within the past 12 months we worried whether our food would run out before we got money to buy more?"	Hager, E.R., Quigg, A.M., Black, M.M., Coleman, S.M., Heeren, T., Rose-Jacobs, R., Cook, J.T., De Cuba, S.A.E., Casey, P.H., Chilton, M. and Cutts, D.B., 2010. Development and validity of a 2-item screen to identify families at risk for food insecurity. Pediatrics , 126(1), pp.e26-e32.
Internet Access	4 items e.g., Do you ever go on-line to access the Internet or World Wide Web, or to send and receive e-mail?	From: HINTS 5, Cycle 4 – Section B: Using the Internet to Find Information, in HINTS 5, Cycle 4 (2020) Methodology Report. https://hints.cancer.gov/docs/methodologyreports/HINTS5_Cycle4_MethodologyReport.pdf
Health Literacy	3 items e.g., How often do you have problems learning about your medical condition because of difficulty understanding written information?	Chew, L.D., Bradley, K.A., & Boyko, E.J. (2004). Brief questions to identify patients with inadequate health literacy. Family Medicine , 36(8): 588-594.
Housing insecurity	2 items e.g., What is your living situation today?	From The Accountable Health Communities (AHC) Health-Related Social Needs (HRSN) Screening Tool. Billioux, A., Verlander, K., Anthony, S., & Alley, D. (2017). Standardized screening for health-related social needs in clinical settings: the accountable health communities screening tool. [Discussion paper]. NAM Perspectives . National Academy of Medicine. https://doi.org/10.31478/201705b

- A sub-set of participants from the intervention group (n=15) will be invited to take part in interviews about their experience in the program, including the cooking classes, recipes, recruitment and engagement. We will also try to understand if and what structural barriers they experienced to participating in the study. This will help provide us data as to how the program may need to be tailored.
  - Participants will be offered the opportunity to participate in the interviews while they are still enrolled in the program or immediately after completing the post-survey.
  - They will give consent by texting or emailing us their interest in participating and then scheduling an interview.
  - Participants will receive a \$25 gift card for their time.
  - The approximately 30-45-minute interviews will be conducted by trained UTHHealth staff and will take place via WebEx.
  - All interviews will be recorded for transcription and subsequent analysis. Spanish interviews will be translated to English by native Spanish speakers. Transcriptions will be coded using standard methods through Dedoose software and deductive thematic analysis will be conducted.
- All patient data will be stored in REDCap and interviews will be saved on the secured share drive.
- Participants will be allowed to contact the principal investigator with any questions. Participants will be allowed to leave the project at any time.

## Data and Safety Monitoring

- There are few adverse events expected. Since the classes involve cooking in a participant's home kitchen, there might be injuries with use of knives, other cooking utensils, stoves, and ovens. Participants assume all risk associated with participating in the culinary medicine classes.

- If adverse events occur, an adverse events form will be completed and submitted to the IRB.

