## Study Design

- This study is a pilot study with a quasi-experimental design using assigned intervention and control clinics.
- Study participants will be evaluated prior to and immediately after the program via pre and post survey.
- EMR data will be reviewed at baseline and completion of program
- This one-year project will include:
  - a) conducting the virtual CM program for approximately 66 intervention patients with diabetes receiving care at UT Physician Clinics serving the Acres Homes neighborhood in Houston
  - b) conducting program evaluation (pre- and post-test surveys and EMR data) using data from those 66 intervention participants and 66 control participants recruited from UT Physicians clinics outside of the Acres Homes service area
- The pre-post survey will evaluate participants’ dietary behaviors, nutrition knowledge, cooking skills and behaviors along with demographic information. The EMR data will evaluate improvements in clinical data: HbA1c, Body Mass Index, Blood Pressure, HDL, LDL and Triglycerides. The results will be used to determine if virtual CM education can be effective in improving certain health outcomes, dietary behaviors and cooking-related constructs.
- There are a few minimal risks known to taking part in this study. Knives will be utilized raising the risk for minor cuts. Stove tops, ovens, microwaves, and other kitchen equipment will be utilized raising the risk for minor burns. Food items containing known allergens will be utilized raising the risk for allergic reaction. We anticipate participation in this study to be of minimal risk and do not expect our program or surveys to cause emotional distress.

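### The protocol states no method for eliciting adverse events, and its monitoring section does not carry over the allergic-reaction risk named in Study Design

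*Combined protocol and SAP*

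**What the plan says.** Study Design names three risks: minor cuts, minor burns and allergy. On the third it says "Food items containing known allergens will be utilized raising the risk for allergic reaction". It then states "We anticipate participation in this study to be of minimal risk".

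Data and Safety Monitoring is the only section on safety. As examples of what may occur in a home kitchen it says "there might be injuries with use of knives, other cooking utensils, stoves, and ovens", with no mention of allergy. Its recording rule is one sentence: "If adverse events occur, an adverse events form will be completed and submitted to the IRB". It gives no definition, grading, collection window or person responsible for asking.

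Study Procedures describes several contacts, none tied to safety:

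- In class: "Participants will cook and engage virtually (with video and sound on) from their home kitchens via the digital platform".
- Between classes: "UTHealth staff will call patients the day before class and send a text reminder 2 hours prior to the class start time".
- Before and after the program: the "surveys will collect information on 1) dietary intake, 2) cooking skills, 3) cooking-related psychosocial constructs, 4) diabetes management, and 5) demographics".
- For 15 intervention participants: "interviews about their experience in the program, including the cooking classes, recipes, recruitment and engagement".

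Data handling and record keeping lists HbA1c, body mass index, blood pressure and lipids for abstraction from the medical record, and states no safety use of that record. Statistics plans no adverse-event summary.

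**The concern.** The exposure is cooking and eating at home, and much of it is out of staff view. Study Procedures sizes each recipe for a household of four and supplies further recipes for use beyond the classes. A reaction some hours after a meal, a burn when a dish is cooked again, or an event in someone who has stopped attending will not be seen on the class video. As the plan is written, such an event reaches a form only if the participant happens to mention it.

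Information not collected at the time cannot be recovered at analysis. The study is a pilot with feasibility among its goals (Objectives), and Publication Plan says it should supply preliminary data for a full-scale trial. A small number of forms could mean few events or poor capture, and the pilot would have no way to tell which.

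**Working it through.** The documents give no adverse-event rate, safety threshold or safety sample size, so there is no stated figure to reproduce. The check has two parts.

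**1. Where could an event be picked up?**

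| Source | Section | Safety content stated |
|---|---|---|
| Live class video | Study Procedures | None, but staff could see an in-class event |
| Day-before call | Study Procedures | None |
| Pre- and post-survey | Study Procedures | Five domains, none on adverse events |
| Interviews (n = 15) | Study Procedures | Injuries and reactions not a listed topic |
| Contact after absence | Compensation | Confirms plan to attend only |
| Follow-up of those missing the last class | Quality control and assurance | Post-survey completion only |
| Medical record extract | Data handling and record keeping | None |
| Form to the IRB | Data and Safety Monitoring | Any adverse event, method of finding it not stated |

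The risk lists compare as follows: Study Design has cuts, burns and allergic reaction; Data and Safety Monitoring has injuries from kitchen tools and heat sources only.

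**2. What would a count of zero mean?**

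Inputs from the documents: 66 intervention participants (Statistics) and five 90-minute sessions (Study Procedures). At full attendance the exposure is 66 × 5 = 330 participant-sessions, or 330 × 1.5 = 495 hours in class.

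With every participant asked and no events, the exact upper limits on per-participant risk are:

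- two-sided 95%: 1 − 0.025^(1/66) = 0.054, or 5.4%;
- one-sided 95%: 1 − 0.05^(1/66) = 0.0444, or 4.4%.

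Now let *s* be the share of affected participants whose event is recorded. The documents give no value for *s*; those below are assumptions. The recorded risk is then *s* times the true risk, so the limit on the true risk is the full-capture limit divided by *s*. The last column takes an assumed true risk of 5% (66 × 0.05 = 3.3 affected participants expected) and gives the chance of recording none, (1 − 0.05*s*)^66.

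| *s* (assumed) | One-sided 95% limit after zero recorded | Chance of zero recorded if true risk is 5% |
|---|---|---|
| 1 | 4.4% | 3.4% |
| 0.75 | 5.9% | 8.0% |
| 0.5 | 8.9% | 18.8% |
| 0.25 | 17.8% | 43.6% |

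The table shows the direction and rough scale of the effect. It does not estimate capture in this study.

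**The case against.** The strongest reply is that this is a small study of cooking classes, that safety is neither a goal in Objectives nor an outcome in the measurement table, and that scheduled questioning is a matter of preference. That is fair as to severity, and nothing here touches the primary outcome. It does not answer the point that the missed events cannot be recovered later and that the contacts needed to ask already exist.

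Several stronger readings are tempting, and the documents do not support them:

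- A reader might infer that events are recorded only when a participant volunteers them. The text is silent on how events are found, and staff could see an in-class cut, burn or reaction on live video.
- A reader might infer that nobody is asked. The consent form and the pre/post survey are listed as attachments and are not available here, so an allergy or adverse-event item in them cannot be ruled out. Only the stated domains can be judged.
- A reader might infer that allergic reactions are excluded from recording, or that the two sections contradict each other. The monitoring list reads as illustrative, and the form rule covers any adverse event. The fault is an omission from the expected events.
- A reader might infer that the minimal-risk statement cannot be checked. It is worded as an expectation, and completed forms would still give a partial check, probably an undercount. Nor does any section say that an absence of forms will be taken as evidence of safety.
- A reader might take 8.9% or 17.8% as estimates. They rest on assumed capture shares and a one-sided limit.

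**Conclusion.** The concern holds as a low-severity gap in data capture. The protocol gives a rule for what to do with an adverse event but no method for finding one, and events outside the live classes would probably be under-recorded. A low count of forms would therefore support the minimal-risk expectation only in part. The allergic-reaction risk in Study Design is not carried into the monitoring section, and the two lists should be reconciled.

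Even with complete questioning, no events in 66 would exclude a per-participant risk only above 5.4% (two-sided). How much wider the uncertainty becomes under the present plan depends on a capture share that the documents do not give. The conclusion assumes that the unseen survey and consent attachments contain no adverse-event question; if the survey does, the gap narrows to the contacts between classes and the missing summary.

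**What to change.** 1. Add one short item, worded identically in both arms, to the post-survey: cut, burn, allergic reaction, other; and whether medical care was needed. Base any between-arm description on this item alone. Questioning one arm more often than the other would bias a comparison that used the additional reports.
2. In the intervention arm, ask the same question at the day-before calls for sessions 2 to 5, each covering the period since the previous session. The call before session 1 precedes any class, and session 5 is covered by the post-survey.
3. Ask it also at the existing contacts with absentees: the confirmation after a missed session (Compensation) and the phone and email follow-up of those who miss the last class (Quality control and assurance).
4. Complete the adverse-event form for any positive answer.
5. Add to Statistics a descriptive summary: the number of intervention participants who were asked, the proportion with at least one event, and its two-sided exact 95% confidence interval.
6. Reconcile the risk lists in Study Design and Data and Safety Monitoring.

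The cost is a slightly longer survey, slightly longer calls and more minor events to log. No new contact is needed. One limit remains: repeated questioning may sharpen recall in the intervention arm, so even the shared post-survey item should be read descriptively.
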